## 10 SAFETY AND ADVERSE EVENTS

### 10.1 Adverse Events/Complications

#### 10.1.1 Potential or Anticipated Adverse Events/Complications - ENTERPRISE

The study is designed to minimize potential risks and complications in the subjects. However the following adverse events associated with intracranial catheterization or intracranial stent placement have been identified as possible (anticipated) adverse events associated with the use of the CODMAN ENTERPRISE® Vascular Reconstruction Device and Delivery System or with the procedure:

- Allergic reaction including, but not limited to, contrast, Nitinol metal and medications
- Aneurysm Bleed or Rebleed
- Aneurysm recanalization or regrowth
- Arm cramps
- Arrhythmia
- Arteriovenous fistula
- Cerebral edema
- Cerebral infarct
- Coil migration or prolapse into normal vessel adjacent to aneurysm
- Cold hands and feet
- Confusion
- Cranial nerve II deficit
- Cranial nerve palsy
- Death
- Deployment Difficulty
- Dissection
- Edema
- Emboli (air, tissue or thrombotic)
- Emergent neurosurgery
- Eyes fixed unable to focus
- Facial numbness
- Failure to deliver stent
- Fever
- Floaters, blurry vision
- Fracture of delivery wire
- Groin Hemorrhage
- Headache
- Hip pain
- Incomplete aneurysm occlusion
- Infection
- Infection at insertion site

- Insertion site hematoma / bleeding
- Injury to normal vessels or tissue
- Intracerebral hemorrhage
- Ischemia
- Laboratory abnormality
- Left, right-sided weakness
- Mid, low back pain
- Myocardial Infarction
- Nausea
- Neck pain
- Neurological deficits
- Not feeling right
- Occlusion of side branch
- Pain at insertion site
- Panic attack
- Perforation
- Pseudoaneurysm
- Radiation effects that include alopecia, cataracts, tissue burns ranging in severity from skin reddening to ulcers and delayed neoplasia
- Renal failure
- Retroperitoneal Hematoma
- Rupture, vessel or aneurysm
- Stenosis of stented segment
- Seizures
- Stent migration / embolization
- Stent thrombosis / occlusion
- Stroke
- Total occlusion of treated segment
- Transient elevation or decrease in blood pressure
- Transient ischemic attack
- Upset stomach
- Vasospasm
- Vessel thrombosis
- Visual field decrease

### 10.1.2 Adverse Event Definitions

An **Adverse Event** is any untoward medical occurrence in a study subject, and which does not necessarily have a causal relationship with the product or treatment; any unfavorable and unintended sign, symptom, or disease temporally associated with the use of the study devices, whether or not considered related to the devices. A preexisting

---

 Radiation risk increases with exposure time and can be reduced by limiting exposure by using sufficient shielding, reducing fluoroscopy times, and modifying X-ray technical factors where possible.

condition should not be reported as an adverse event unless the condition worsens or episodes increase in frequency during the adverse event reporting period.

An **Adverse Device Effect (ADE)** is a device-related Adverse Event.

A **Serious Adverse Event (SAE)** is any significant adverse experience, including those that may be either life-threatening or involving permanent or long term injuries but excluding injuries that are non-life-threatening and/or that are temporary and reasonably reversible. A Serious Adverse Event includes any of the following events that may or may not be considered related to the device;

- Results in Death,
- Is life-threatening,
- Requires inpatient hospitalization or prolongation of existing hospitalization,
- Results in persistent or significant disability/incapacity, or
- Is a congenital anomaly/birth defect

Serious Adverse Events may or may not be related to the device.

An **Unanticipated Adverse Device Effect (UADE)** is defined as any serious adverse effect on health or safety or any life-threatening problem or death caused by, or associated with, a device, if that effect, problem, or death was not previously identified in nature, severity, or degree of incidence in the investigational plan or application (including a supplementary plan or application), or any other unanticipated serious problem associated with a device that affects the rights, safety, or welfare of study subjects may also be considered UADEs.

All Adverse Events, Adverse Device Effects, Serious Adverse Events, and Unanticipated Adverse Device Effect must be recorded, as applicable, on the eCRF.

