## **10.8 Reporting of Adverse Events and Study Device Product Complaints and Device Malfunctions**

As noted in the Table 6, a serious adverse event is to be reported immediately via eCRF but no later than 72 hours after knowledge of the event.

It is the responsibility of the investigators to inform their Institutional Review Board (IRB) of Adverse Events, Serious Adverse Events, Unanticipated Adverse Device Effects, and Device Malfunctions/Deviations as required by their IRB procedure and country law. The sponsor is responsible for sending information on the unanticipated adverse device effect to the regulatory authorities. In the instance of death a copy of the death certificate or other relevant documentation (autopsy report) should be provided. If an autopsy is performed, a copy of the autopsy report may be requested and sent to the regulatory authorities, if required.

If the ENTERPRISE device does not perform as expected, but is without any adverse event, the investigator must document on the appropriate eCRFs, and notify the Sponsor within 10 business days. If the study device is not implanted it must be retained at the site until the Sponsor provides instructions on the return process.

If a serious adverse event is related to the performance of the study device, the Sponsor must be notified immediately via eCRF immediately but no later than 72 hours after knowledge of the event. If the study device was not implanted it must be retained at the site until the Sponsor provides instructions on the return process.

Non-Serious adverse events are to be reported via eCRF within 10 days of learning of the event.

If a device other than the study investigational ENTERPRISE stent malfunctioned, follow the manufacturer's instructions, and do not report as a product complaint on the eCRF and/or do not complete the study Device Malfunction eCRF.

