**Table 6: Report requirements of adverse events, product complaint and device malfunctioning**

Classification	Reporting time	Type of report
Death	Notify Sponsor as soon as possible but no later than 72 hours of learning of event. Notify IRB as required	eCRF
Unanticipated Adverse Device Effects (UADE)	Notify Sponsor as soon as possible but no later than 72 hours of learning of event. Notify IRB as required	eCRF
Serious Adverse Events (whether related to the performance of the study device or not)	Notify Sponsor as soon as possible but no later than 72 hours of learning of event. Notify IRB as required	eCRF
Non-serious Adverse Events	Notify Sponsor within 10 business days of learning of event. Notify IRB as required	eCRF
Study Device Product Complaint or Device Malfunction With or Without Adverse Event	Notify Sponsor within 10 business days of learning of event. Notify IRB as required	eCRF

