### **15.3 Termination of Center by Sponsor**

The Sponsor reserves the right to terminate an investigational site; this may include for any of the following reasons (but not be limited to):

- The center cannot comply with the requirements of the protocol
- Repeated failure to complete eCRFs in a timely manner
- Failure to report Serious Adverse Events within within 10 business days of knowledge
- Loss of or unaccounted for investigational device inventory
- Repeated protocol deviations/violations
- Investigator leaves the institution and no adequate replacement

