10.4 Primary and Secondary Endpoint Analyses

Protocol specified tests of hypotheses of the primary endpoints will not be performed due to the study terminating early for low enrollment. Descriptive analyses of the primary effectiveness and primary safety endpoint will be conducted in the mITT Analysis Set. Categorical data will be summarized with exact binomial confidence intervals for primary effectiveness and safety endpoints. Continuous data will be summarized with averages by visit and as average change from baseline at each visit.

Unless specified otherwise, the classification of adverse events will be based on the data from study case reported forms (CRFs). In the event the data are not captured or are missing, the DSMB and/or CEC adjudication data will be reported.

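### The SAE definition both excludes and includes reversible, non-life-threatening events that lead to or prolong hospitalization, and no text says which part governs

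*Protocol*

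**What the plan says.** Protocol section 10.1.2 defines a serious adverse event (SAE) in two parts, and Appendix 1 repeats both.

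- The lead sentence covers significant adverse experiences, "including those that may be either life-threatening or involving permanent or long term injuries", and then narrows this: "but excluding injuries that are non-life-threatening and/or that are temporary and reasonably reversible".
- The list beneath has five criteria. Two matter here: "Requires inpatient hospitalization or prolongation of existing hospitalization" and "Results in persistent or significant disability/incapacity, or". Neither requires a threat to life or irreversibility.

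On timing, section 10.8 states that "a serious adverse event is to be reported immediately via eCRF but no later than 72 hours after knowledge of the event". Table 6 agrees for SAEs: "Notify Sponsor as soon as possible but no later than 72 hours of learning of event". Table 6 gives non-serious events 10 business days. Section 10.1.3 says that the investigator's classification decides the reporting procedure and that the sponsor may upgrade it. Section 15.3 gives, among the possible reasons for closing a site, "Failure to report Serious Adverse Events within within 10 business days of knowledge".

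In the SAP, section 10.4 says that, unless specified otherwise, "the classification of adverse events will be based on the data from study case reported forms (CRFs"), with committee data used only when form data are missing or not captured. SAP section 10.4.2.2 plans a table of SAEs and uses the Clinical Events Committee (CEC) for relationship.

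**The concern.** An investigator who applies the lead sentence and one who applies the list can label the same event differently, and each can point to protocol text. Appendix 1 carries the same wording, so checking one place against the other settles nothing.

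Two things depend on the label. One is how soon the sponsor must be told. The other is the SAE count, which belongs to a listed secondary safety endpoint. With a single arm and a descriptive report, that count will be read at face value. A site that follows the exclusion reports fewer SAEs, so the error runs toward a safer-looking device.

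**Working it through.** **1. Apply each part of the definition to events named in protocol section 10.1.1.** Assume none of them is life-threatening.

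| Event | Exclusion clause | Inclusion half of the lead sentence | List |
|---|---|---|---|
| Transient ischemic attack leading to admission | Out | Not covered | In (hospitalization) |
| Access-site hematoma that resolves but prolongs the stay | Out | Not covered | In (prolongation) |
| Permanent cranial nerve palsy or visual field loss | Out if 'or' is applied | In (permanent injury) | In if judged persistent or significant disability |

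**2. Test both readings of 'and/or'.** Read as 'and', the clause removes only injuries that are both non-life-threatening and reversible. The first two rows stay out and the third is no longer excluded. Read as 'or', being non-life-threatening is enough by itself, and all three rows are out. The conflict with the hospitalization criterion therefore survives either reading. The conflict over permanent deficits needs the 'or'.

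**3. Difference in the reporting deadline.** Inputs are the two Table 6 limits; no public holidays are assumed.

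- SAE limit: 72 hours = 3 days.
- Non-serious limit: 10 business days = 12 calendar days if the site learns on a Sunday, 13 on a Saturday, 14 on a weekday.
- Difference: 12 − 3 = 9 days, up to 14 − 3 = 11 days.
- Ratio: (12 × 24)/72 = 288/72 = 4.0, up to (14 × 24)/72 = 336/72 = 4.7.

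The text of section 10.8 gives non-serious events 10 days rather than 10 business days. On that wording the difference is 10 − 3 = 7 days. These are differences between the latest permitted dates, not expected delays.

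**4. Follow the label to the SAE table.** The investigator classifies (protocol 10.1.3). The sponsor may upgrade but need not. The CEC's stated task is relationship to device, procedure or disease (protocol 10.9.1); seriousness is not mentioned. The SAP falls back on committee data only where form data are absent. A completed entry of non-serious is not absent, so it stands.

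**The case against.** The strongest reply is that this is a drafting slip with limited reach, and much of that stands.

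- **Permanent injury.** A reader might infer that lasting deficits are plainly excluded. They are not: the first half of the same sentence includes permanent or long-term injuries, and the disability criterion points the same way. The clean conflict is over reversible events with a hospital stay.
- **Section 15.3.** A reader might infer that the protocol tolerates SAE reports at 10 business days. Section 15.3 is a discretionary, open-ended list of reasons to close a site, not a second deadline. It also names repeated deviations, and section 11.6 requires the sponsor to secure compliance or end the investigator's participation. The 72-hour limit is stated consistently for SAEs, unanticipated device effects and deaths. What remains is a mismatch of figures.
- **Data and Safety Monitoring Board.** It is tempting to say that the board would learn of harms later. The protocol has it meeting periodically and gives it no 72-hour notice, so this cannot be shown.
- **Earlier studies.** Differences in SAE rates among the sponsor's earlier studies might be read as the size of the misclassification. Those rates count device- or procedure-related events already called SAEs, in different populations, under definitions the documents do not give. They do not measure it.
- **Other capture.** All adverse events go on the case report form and are tabulated. Bleeding that lengthens the stay is its own endpoint, and NIHSS and mRS are scored at visits. Source data are verified. Harms would be mislabelled or reported later, not lost.
- **Timing.** The SAP says that the study is ending early with descriptive output only. No hypothesis test is at risk, and an amendment now would affect little new data.

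None of this says which half of the definition governs, and none of it makes review of seriousness routine.

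**Conclusion.** The point holds as a contradiction within the SAE definition, in both places where it appears. It should be corrected, and the correction is cheap. For an event labelled non-serious on the strength of the exclusion, the permitted reporting time lengthens by up to 9 to 11 calendar days under Table 6 (7 days under the text of section 10.8), and the event can drop out of the SAE table.

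The documents do not show how many events are affected, so no bias in the SAE rate can be given; its direction is toward fewer SAEs. The primary safety endpoints are untouched: SAP section 10.4.1.2 takes major ipsilateral stroke or death from board-adjudicated data and in-stent stenosis from the core laboratory, and neither uses the SAE label.

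This rests on two assumptions: that at least some sites apply the exclusion as written, and that classification in SAP section 10.4 includes seriousness. The period in section 15.3 is a minor inconsistency.

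**What to change.** 1. In protocol section 10.1.2 and Appendix 1, delete the exclusion clause and replace the lead sentence with *A Serious Adverse Event is any adverse event that:* followed by the five existing criteria. Deleting the clause alone is not enough. The remaining lead sentence would still turn on an undefined notion of significance, and the list would still read as examples.
2. Before the final tables, check every event recorded as non-serious against the five criteria. State in the SAP that the SAE table follows this check, and report how many events changed label. With the study closing, this step and a letter to sites do most of the work.
3. Minor: reconcile the SAE period in section 15.3 with section 10.8 and Table 6, and the two versions of the non-serious limit in section 10.8 and Table 6.

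The cost is a short text change in two places, one pass through the recorded events, a somewhat higher SAE count and a few more expedited reports.

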**Note:**

- Recanalization is not considered an adverse event since this is not an untoward medical occurrence to the subject, but rather an anticipated occurrence in the evolution of aneurysms
- Adverse events include abnormalities in physiological testing or physical examination that require clinical intervention or further investigation.
- Subjects should be encouraged to report AEs spontaneously or in response to general, non-directed questioning (e.g. "how has your health been since the last visit?"). Any time during the clinical investigation, the subject may volunteer information that resembles an

AE. If it is determined that an AE has occurred, the investigator should obtain all the information required to complete the AE form.

### **10.1.3 Adverse Event Severity and Causal Relationship Ratings**

The Investigator will record the nature, severity, treatment and outcome of the AE, and will determine the relationship to device, procedure or underlying disease. This classification of the event determines the reporting procedures to be followed. The sponsor may upgrade the classification as required for reporting purposes.

For purposes of this protocol, the following definitions will apply.

#### ***Adverse Event Severity Rating***

The following categories of adverse event severity are to be used:

- Mild: Awareness of sign or symptom that does not interfere with the subject's usual activity or is transient, resolved without treatment and with no sequelae,
- Moderate: Interferes, but does not hinder, the subject's usual activity and/or may require treatment,
- Severe: Symptom(s) causing severe discomfort and significant impact on the subject's usual activity and requires treatment or intervention.

#### ***Causal Relationship Rating***

The causal relationship to study device, study procedure, and underlying disease will be evaluated as follows:

- Definitely Related: The adverse event is clearly related to the test product.
- Probably Related: The adverse event is temporally associated and plausibly related to the product/procedure but there are also potential alternative explanations, though the alternatives are not likely.
- Possibly Related: The adverse event may be related, scientifically plausible, but there are also alternative explanations.
- Unlikely Related: The adverse event is doubtfully related.
- Not Related: The adverse event is clearly not related. The adverse event is most plausibly explained by the subject's underlying medical condition or their concomitant therapy, or the adverse event has no

plausible relationship to study treatment, or the adverse event has no plausible biological relationship to the study treatment.

## **10.2 Unanticipated Adverse Device Effects**

The investigator shall submit to the Sponsor a report of any unanticipated adverse device effect (UADE) occurring during the investigation as soon as possible but no later than 72 hours after the investigator first learns of the effect. Additionally, if a UADE occurs in a device other than the study device (ENTERPRISE), follow FDA and manufacturer's instructions for reporting the UADE.

Unanticipated adverse device effects are defined as any serious adverse effect on health or safety or any life-threatening problem or death caused by, or associated with, a device, if that effect, problem, or death was not previously identified in nature, severity, or degree of incidence in the investigational plan or application (including a supplementary plan or application), or any other unanticipated serious problem associated with a device that affects the rights, safety, or welfare of study subjects may also be considered UADEs.

If the Sponsor determines that an unanticipated adverse device effect presents an unreasonable risk to subjects, all or parts of investigations presenting that risk will be terminated as soon as possible. Termination will occur not later than five working days after the Sponsor makes this determination and not later than fifteen working days after the Sponsor first receives notice of the effect.

## **10.3 Management of Post-procedure Symptoms**

If clinical symptoms deteriorate, the subject must be seen and assessed by the study investigator immediately. This does not exclude the subject from the study and follow-up should continue. All subjects entered into the study remain in the study until the 24 month post procedure study follow-up visit has been reached.

If a subject presents with an adverse event at the 24 month study visit, he/she will receive appropriate treatment for that condition. If the subject's condition precludes him or her from undergoing any 24 month evaluation specified by the protocol, the subject would be discharged from the study after the Investigator documents in the subject's medical record that a stable clinical endpoint has been reached, or that the subject's status is not associated with the device or procedure.

Following the 24 month study visit, the subject will be discharged from the study. However, if at the 24 month study visit the investigator determines there are indications of delayed hydrocephalus or in-stent stenosis

occurring, additional follow-up may be required, including MRI or CT at the Investigator's discretion. If this occurs, the investigator will determine the additional follow-up required at that time and inform the study sponsor.

## **10.4 Subject Death**

Subject death during the investigation must be reported to the Sponsor as soon as possible but no later than 72 hours of the investigator's knowledge of the death. Notification of death must include a brief statement of the pertinent details and be signed by the investigator. A copy of the death records, death certificates and an autopsy report (if performed) must be sent to the Sponsor.

## **10.5 Adverse Event Reporting Period**

### **10.5.1 Adverse Event Reporting for Angiographic Screening Failure**

Any subject, who had an angiogram, but was not entered, will be followed for the period 72 hours following the end of the angiographic procedure to determine study angiographic eligibility, or until discharge, whichever comes first, or to resolution of any adverse event, whichever is longer. Any AEs that occurred from the time written consent was obtained through the period described must be entered into the eCRF database.

### **10.5.2 Adverse Event Reporting for Entered Subjects**

The adverse event reporting period for this study begins at the time the study informed consent is signed and ends at the twenty-four month follow-up unless noted otherwise in Section 11.3. Adverse events that occur in subjects during the adverse event reporting period must be entered into the eCRF database. All required treatments and outcomes of the adverse event must be recorded.

## **10.6 Recording Adverse Event Information**

The investigator is to report all directly observed adverse events and all adverse events spontaneously reported by the subject via eCRF. In addition, each subject in the study will be questioned about adverse events on the day of hospital discharge, and at thirty (30) days, six (6) months, twelve (12), eighteen (18) months, and twenty-four (24) month follow-ups after the index procedure. All required treatments and outcomes of the adverse event must be recorded.

